Sequential nephron blockade, or combination diuretic therapy, with a loop and thiazide-type diuretic is a frequently used strategy to overcome diuretic resistance caused by hypertrophy of the distal convoluted tubule.⁴ In healthy patients, approximately 25% of sodium is reabsorbed proximally at the ascending loop of Henle and 5% of sodium is reabsorbed at the distal convoluted tubule. With increasing doses of loop diuretics, a compensatory increase in sodium reabsorption occurs via the sodium chloride cotransporter at the distal convoluted tubule.⁴ Adding a thiazide-type diuretic, such as metolazone limits this distal reabsorption and therefore restores effectiveness of diuretic therapy. Most studies examining combination diuretic therapy in AHDF are retrospective and evaluate a limited number of patients (1 to 45 patients).⁶⁻¹³ Overall, combination diuretic therapy has been found to be safe and efficacious in increasing urine output and decreasing weight. The most common side effect noted in these studies is hypokalemia. Of the available thiazide diuretics, one has not been found to be more effective than another; however, metolazone is often used due to its potency and long duration of action (up to 20 hours).¹⁴

Based on this observed synergy, combination therapy with furosemide and metolazone is routinely prescribed in patients presenting with ADHF without adequate diuresis from loop diuretics alone. It has been recommended to administer the thiazide-type diuretic one hour

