Adults aged 18 to 89 years are eligible for enrollment if they present within the previous 48 hours with ADHF to the advanced heart failure service at UMMC. ADHF will be defined on the basis of the presence of at least one symptom (dyspnea, orthopnea, cough, or edema) and one sign (rales, peripheral edema, ascites, jugular venous distention, or pulmonary vascular congestion on chest radiography) of heart failure. Additional eligibility criteria are receipt of an oral loop diuretic prior to admission and plan to administer furosemide 120 – 200 mg IV bolus twice daily over the next 24 hours with additional diuresis deemed necessary. Patients are to be excluded if they have cirrhosis, an estimated glomerular filtration rate (GFR) less than 10 mL/min/1.73m2, need for concurrent renal replacement therapy, or if they were prescribed metolazone prior to admission. Non-English speaking patients and patients that could not provide consent and do not have a legally authorized representative to provide consent will also be excluded.

Randomization and Treatment Assignments:

Patients will be randomized in a 1:1 ratio to a pre-dosing strategy (metolazone 5 mg orally dosed 60 minutes prior to furosemide 120 – 200 mg IV bolus) or a concurrent dosing strategy (metolazone 5 mg dosed simultaneously with furosemide 120 – 200 mg IV bolus). All treatment during the 24-hour study period will be open-label at the discretion of the treating physician. Patients enrolled in the study can receive additional IV boluses up to every 6 hours during the 24-hour study period. If per the treating physician, patients required additional doses of metolazone, switch to furosemide IV continuous infusion, titration of IV inotrope or IV vasodilator, or renal replacement during the 24-hour study period, the appropriate therapy will be ordered and the patient will be excluded from the study at that time. Patients will be followed until discharge.

Endpoints:

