The primary endpoint will be total urine output (mL) 24 hours post-metolazone dose. The total urine output will be collected and entered into EPIC electronic medical record by nursing staff and the value will be collected by study investigator during chart review. Additional prespecified secondary endpoints that will be assessed 24 hours post-metolazone dose include: net fluid balance (mL), change in weight (kg), change in SCr (mg/dL), proportion of patients with acute kidney injury (AKI) (defined as an increase in SCr by \geq 0.3 mg/dL or \geq 50% from baseline), hypokalemia (K <4.0 mEq/L), hypomagnesemia (Mg <2.0 mEq/L), and hyponatremia (Na 125 - 135 mEq/L 24).

Statistical Analysis:

We calculated that 126 patients would have to be enrolled in order to achieve 80% power to detect an effect size of 500 mL. Given that this was a pilot study, our target patient enrollment will be 30 patients as this was felt to be a feasible number of patients to enroll during the study period. Descriptive statistics will be used to characterize data. When target enrollment is reached, the primary endpoint will be analyzed using student t-test. For other variables and outcomes, data will be analyzed using student t-test or chi-square/Fisher's exact test as appropriate.

References:

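### Electrolyte events are scored on the 24-hour value alone, so the reported proportions mix abnormality present before metolazone with new or worsened abnormality

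*Combined protocol and SAP*

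**What the plan says.** The Endpoints section introduces the list with "Additional prespecified secondary endpoints that will be assessed 24 hours post-metolazone dose include". Two items are explicit change scores, "change in weight (kg), change in SCr (mg/dL". AKI is also relative to a starting value: "increase in SCr by \geq 0.3 mg/dL or \geq 50% from baseline". The next three items are "hypokalemia (K <4.0 mEq/L), hypomagnesemia (Mg <2.0 mEq/L), and hyponatremia (Na 125 - 135 mEq/L 24". These are absolute ranges with no pre-dose term. The baseline wording belongs to AKI only, because its parenthesis closes before hypokalemia begins: "50% from baseline), hypokalemia (K <4.0 mEq/L".

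The Study Participants section sets no limit on potassium, magnesium or sodium at entry. Its exclusions begin "Patients are to be excluded if they have cirrhosis, an estimated glomerular filtration rate (GFR) less than 10 mL/min/1.73m2" and go on to renal replacement therapy, earlier metolazone, language and consent. It does require previous diuretic exposure: "Additional eligibility criteria are receipt of an oral loop diuretic prior to admission". The background text says of combination therapy: "The most common side effect noted in these studies is hypokalemia".

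Under Statistical Analysis, the binary outcomes go to chi-square or Fisher's exact tests with no baseline adjustment, and target enrolment is 30.

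**The concern.** A low value at 24 hours can arise in three ways: it was low before dosing and stayed low, it became low, or it was low and fell further. The written rule does not separate these. All patients were taking a loop diuretic before admission, so low values before the study dose are plausible.

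A reader of the results is likely to take a hypokalemia or hyponatremia proportion as something that happened after dosing. The same figure would be a natural planning input for a larger trial, where a mixture of prevalence and incidence would mislead. With about 15 patients per arm, the arms may also differ by chance in how many patients were already low.

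**Working it through.** No figure in the plan depends on these definitions, so there is none to reproduce. The check has four parts.

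**1. The literal rule applied to single patients (values in mEq/L)**

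| Before metolazone → 24 h | Direction | Plan's rule |
|---|---|---|
| K 3.7 → 3.9 | rising | event |
| Na 132 → 134 | rising | event |
| Na 123 → 126 | rising | event |
| Na 130 → 123 | falling | not counted |
| Na 136 → 123 | falling | not counted |

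The last three rows arise because the sodium range is closed at both ends (125–135). Magnesium has the same form of definition as potassium. A patient who was low before dosing but is out of range at 24 hours is not counted, so the issue concerns only those still in range. The assessment time could mean the value at 24 hours or any value up to 24 hours; neither reading brings in the pre-dose value. The stray 24 after the sodium range may be a reference mark and is not relied on.

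**2. Chance imbalance at entry**

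Inputs: 30 patients at 1:1, so 15 per arm (documents); proportion p already low before dosing (assumed). With X₁ and X₂ independent Binomial(15, p), the quantity is P(|X₁ − X₂| ≥ 3).

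| p | 10% | 20% | 30% | 35% | 50% |
|---|---|---|---|---|---|
| P(difference ≥ 3) | 12% | 25% | 32% | 34% | 36% |

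**3. How mixed the proportions could be with no drug effect**

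All inputs here are assumed: bivariate normal values before dosing and at 24 hours, no mean shift, 1,000,000 simulated patients per setting, rounding to 1 (Na) or 0.1 (K).

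| | Na: mean 135–139, SD 4, correlation 0.6–0.9 | K: mean 3.9–4.3, SD 0.5, correlation 0.3–0.7 |
|---|---|---|
| Patients scored as events | 19–55% | 24–54% |
| Share of events already in range before dosing | 49–87% | 37–77% |
| Share of events unchanged or higher | 29–55% | 21–44% |
| New events, as a share of patients | 5–15% | 10–20% |

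If K falls by 0.3 mEq/L in every patient, 32–66% of events are still pre-existing.

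**4. Which event definition separates the arms**

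Same K assumptions, 15 v 15, no shift in one arm and −0.3 mEq/L in the other:

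| Definition | Difference between arms | Fisher power |
|---|---|---|
| 24-hour value only (plan) | 22–24 points | 12–13% |
| New onset only | 11–16 points | 5–9% |
| New onset, or further fall ≥ 0.3 if already low | 19–28 points | 11–20% |

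New onset alone does worse than the plan's rule because it discards patients who were low and were kept low or driven lower. The third definition does about as well as the plan's rule or better, but its result depends on the minimum fall chosen; 0.3 is only an illustration.

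**The case against.** The strongest reply is that 24-hour prevalence is a legitimate measure of clinical status, that the plan does not call these events new or treatment-emergent, and that randomisation protects the comparison. All of this stands. Fisher's test already allows for chance imbalance, and with a correlation below 1 only part of an imbalance at entry persists to 24 hours. That is why the 24-hour proportions should stay.

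Four stronger readings are tempting, and the documents do not support them.

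- *Pre-existing cases hide a real difference between arms.* Suppose b is the proportion low at entry, q₁ and q₂ are the new-onset risks, and low values persist equally often in both arms. The 24-hour difference is then (1 − b)(q₂ − q₁). For 20% v 50% new onset it is 0.9 × 30 = 27 points at b = 10% and 0.5 × 30 = 15 points at b = 50%. This result requires that the strategy has no effect on patients who are already low. When the shift acts on every patient, as in part 4, the plan's rule shows the larger difference than new onset alone.
- *Many counted events pre-date the drug.* This may be so, but the documents give no baseline or event rates. The percentages in part 3 rest entirely on assumed distributions.
- *The rule misattributes harm to combination therapy.* Both arms receive the same metolazone dose, so the trial compares timing. No event definition would allow that attribution.
- *The rule misses a large fall such as Na 142 to 136.* It does, but so would a baseline-referenced rule with the same cut-off. That is a cost of dichotomising, and a separate matter.

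**Conclusion.** The point holds as one of interpretation. The three electrolyte proportions combine abnormality present before dosing with new or worsened abnormality, and nothing in the plan lets a reader separate them. This rests on the text alone.

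Its size cannot be taken from the documents. Under the assumption that 20–50% of patients are low at entry, the arms differ by 3 or more such patients in 25–36% of trials of this size. Under the assumed distributions, between about a third and most of the counted events could have been in range before dosing. There is no systematic bias between arms. No definition examined exceeds about 20% power for the illustrated potassium shift, so the choice would not rescue or sink the comparison.

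Severity is minor: these are secondary endpoints in a self-described pilot of 30 patients.

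**What to change.** Add a short statement to the Endpoints section:

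- Abstract the last potassium, magnesium and sodium values before metolazone from the chart.
- Keep the stated 24-hour proportions as they are.
- Beside them, report by arm a baseline-by-24-hour shift table for each electrolyte, and the proportion with new-onset or worsened abnormality. Worsening in a patient already low means a further fall of at least a minimum fixed in advance. Do not replace the current endpoint with new onset alone.
- For sodium in this added analysis, count every value at or below the stated upper limit of 135, including values under 125. Then 123 → 126 is not an event, 136 → 123 is a new event, and 130 → 123 counts as worsened if the fall of 7 reaches the minimum.
- State how many patients in each arm lack a pre-dose value.

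The cost is slightly more chart abstraction; AKI already requires a baseline creatinine. Patients with no pre-dose value cannot be classified in the added analysis. Treatment, eligibility and sample size do not change.

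### The hypomagnesemia cut-off of 2.0 mEq/L equals 2.43 mg/dL; the unit is probably wrong, and as written the endpoint would probably count most patients in both arms as events

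*Combined protocol and SAP*

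**What the plan says.** In the combined protocol and SAP, Methods, Endpoints, the list of secondary outcomes opens with "Additional prespecified secondary endpoints that will be assessed 24 hours post-metolazone dose include". It includes "hypomagnesemia (Mg <2.0 mEq/L", next to "hypokalemia (K <4.0 mEq/L". Creatinine, in the same sentence, is in mg/dL; potassium, magnesium and sodium are all in mEq/L. Acute kidney injury is the only binary outcome in the list defined against a patient's own starting value ("50% from baseline"); the magnesium outcome is a single threshold at 24 hours.

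The documents give no reason for the magnesium threshold, no laboratory reference range, no mg/dL equivalent, no expected magnesium level or event rate, and no statement of the unit in which the hospital laboratory reports magnesium.

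On size and analysis, Statistical Analysis says "our target patient enrollment will be 30 patients", and Randomization and Treatment Assignments says "Patients will be randomized in a 1:1 ratio", which gives 15 per arm. For outcomes other than the primary, "data will be analyzed using student t-test or chi-square/Fisher's exact test as appropriate".

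**The concern.** For potassium, a singly charged ion, mEq/L and mmol/L are the same number. For magnesium they differ by a factor of two, and the conversion to mg/dL is different again. A threshold carried across an electrolyte list with one common unit can therefore be right for one ion and wrong for another. Here the number 2.0 means two different things in mEq/L and mg/dL, about 22% apart (2.43 / 2.0 = 1.215).

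A chart abstractor who applies the definition literally uses 2.43 mg/dL and may label as hypomagnesemic many patients whose magnesium is not low. If instead the record shows mg/dL and the abstractor compares it directly with 2.0, the reported definition is not the one applied. A 30-patient pilot will be read mainly for its descriptive rates, so what is at stake is a misleading safety rate for the combination and, secondarily, a comparison between arms that carries little information.

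**Working it through.** **The plan's own figure.** The plan states no event rate or power for hypomagnesemia, so there is nothing to reproduce for this endpoint. Its one sample-size figure ("126 patients would have to be enrolled in order to achieve 80% power to detect an effect size of 500 mL") concerns urine output and does not bear on this point.

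**Inputs.** From the documents: cut-off 2.0 mEq/L, 30 patients, 1:1 allocation (15 per arm), Fisher's exact test. Physical constants: atomic mass of magnesium 24.305, valence 2. Assumed, and not in the documents: 24-hour magnesium is normally distributed with mean 1.9 to 2.2 mg/dL and SD 0.2 to 0.3 mg/dL. A mean of 2.3 is used as a stress case.

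**Step 1: conversion.**
- mg/dL = (mEq/L ÷ 2) × 24.305 ÷ 10
- 2.0 mEq/L: (2.0 ÷ 2) × 24.305 ÷ 10 = 2.4305, i.e. 2.43 mg/dL (1.0 mmol/L)
- In reverse, 2.0 mg/dL: 2.0 × 10 ÷ 24.305 × 2 = 1.65 mEq/L

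**Step 2: share of patients counted as events.** Share = Φ((cut-off − mean) ÷ SD).

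| Mean, SD (mg/dL) | Below 2.43 mg/dL (as written) | Below 2.0 mg/dL |
|---|---|---|
| 1.9, 0.2 | Φ(2.65) = 99.6% | Φ(0.50) = 69.1% |
| 1.9, 0.3 | 96.1% | 63.1% |
| 2.0, 0.2 | 98.4% | 50.0% |
| 2.0, 0.3 | 92.4% | 50.0% |
| 2.1, 0.2 | 95.1% | 30.9% |
| 2.1, 0.3 | 86.5% | 36.9% |
| 2.2, 0.2 | Φ(1.15) = 87.5% | Φ(−1.00) = 15.9% |
| 2.2, 0.3 | Φ(0.77) = 77.9% | 25.2% |

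The ranges are therefore about 78 to 100% as written and 16 to 69% at 2.0 mg/dL. In the stress case, mean 2.3 with SD 0.20 to 0.35, the written cut-off still counts 74.3% down to 64.5%.

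**Step 3: ability to separate the arms.** Exact two-sided Fisher power at the 0.05 level, 15 per arm, found by enumerating all outcomes. The first arm has mean 1.9 to 2.2 mg/dL, SD is 0.2 or 0.3, and the second arm's mean is lower by the shift shown.

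| Shift (mg/dL) | As written | At 2.0 mg/dL |
|---|---|---|
| 0.1 | 0 to 3.5% | 4.4 to 8.9% |
| 0.2 | 0 to 8.1% | 14 to 39% |

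Sample size is the same in both columns, so the difference between them comes from the cut-off. The low values in the right-hand column come from having 15 per arm. As a further guide, if one arm is 15/15, the other must be 10/15 or fewer to reach significance (p = 0.042); 11/15 gives p = 0.100.

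**The case against.** The conversion cannot be disputed, but much of what one might build on it can.

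- **Upper limit of normal.** A reader might infer that the cut-off lies at or above the upper limit of normal. The documents give no reference range. If the upper limit were 2.2 or 2.4 mg/dL (1.81 or 1.97 mEq/L), the statement would be true; at 2.6 mg/dL (2.14 mEq/L) it would be false.
- **Nearly every patient an event.** This too depends on assumption. About 22% are non-events at mean 2.2 and SD 0.3, and 26 to 35% at mean 2.3. Higher magnesium is possible, because patients are excluded for renal function only when GFR is below 10 and the documents do not address magnesium replacement. Most patients is as far as the material goes.
- **Arms that cannot be separated.** The arms differ only by 60 minutes in the timing of one metolazone dose, so a large magnesium difference is not expected, and with 15 per arm small differences are hard to detect under any cut-off. At higher means the written cut-off is not always the worse one: for means of 2.4 versus 2.1 mg/dL with SD 0.25, power is 46% as written and 36% at 2.0 mg/dL. Little ability under the assumed range is supportable; none is not.
- **Intended unit.** That 2.0 was meant in mg/dL is an inference. The neighbouring potassium threshold is a similarly round number in mEq/L, and if the laboratory reports magnesium in mEq/L there is no mismatch at abstraction.
- **Reach.** This is one of several secondary endpoints. No treatment or stopping rule uses the threshold, and the magnesium values are in the chart and can be re-scored.

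All of this stands, and it limits the wording and the severity. It does not explain the threshold: nothing in the documents supports 2.43 mg/dL as a definition of low magnesium.

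**Conclusion.** The point holds in a limited form. It is certain that the written threshold equals 2.43 mg/dL and that the same number in mg/dL would be 1.65 mEq/L. It is probable, but not documented, that the unit is wrong. Under the assumed distributions the written definition would label most patients in both arms hypomagnesemic, at a rate well above that given by 2.0 mg/dL, and would have little power to distinguish the arms. The main harm is a misstated safety rate; the loss of power is secondary and partly due to the pilot's size. The documents do not support reading this as an endpoint that is bound to be uninformative, or as a threat to the trial's main result. Severity is moderate: one secondary endpoint is affected, and urine output, eligibility, randomization and sample size are untouched.

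**What to change.** Before any outcomes are tabulated, check the threshold against the hospital laboratory's reporting unit for magnesium and its reference range. Then correct the endpoint definition in one of two ways:

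- if mg/dL was intended: Mg <2.0 mg/dL (1.65 mEq/L);
- otherwise: the laboratory's own lower limit of normal, stated in mEq/L.

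State the unit and its conversion once, and use that single definition in chart abstraction and in reporting. Timing matters, because choosing the unit after seeing the rates would look post hoc.

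The cost is one line of text and, if values have already been abstracted, re-scoring them. No new patients or data are needed. The reported hypomagnesemia rate would be expected to be lower than under the written definition. This changes an outcome definition only, not treatment.

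### Hyponatremia is defined as sodium 125 to 135 mEq/L, so read literally a 24-hour sodium below 125 counts as no event

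*Combined protocol and SAP*

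**What the plan says.** The Endpoints section gives a single list of secondary outcomes, all assessed 24 hours after the metolazone dose. Acute kidney injury enters as a "proportion of patients with acute kidney injury (AKI", with thresholds that are open toward larger rises in creatinine. The electrolyte outcomes follow: "hypokalemia (K <4.0 mEq/L), hypomagnesemia (Mg <2.0 mEq/L", and last "and hyponatremia (Na 125 - 135 mEq/L 24".

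No other endpoint uses sodium. There is no separate category for values below 125 and no continuous change in sodium.

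Study Participants sets the baseline exclusions, starting with "Patients are to be excluded if they have cirrhosis, an estimated glomerular filtration rate (GFR) less than 10 mL/min/1.73m2" and going on to renal replacement therapy, prior metolazone, language and consent. Sodium is not among them. Randomization and Treatment Assignments lists the events during the 24 hours that take a patient out of the study, and sodium is not among those either.

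On size, the plan states "Patients will be randomized in a 1:1 ratio" and "our target patient enrollment will be 30 patients". Binary outcomes are to be compared by chi-square or Fisher's exact test.

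**The concern.** An adverse-outcome definition should not stop counting patients as their values get worse. This one does. A patient at 126 is a case and a patient at 124 is not. On the plain reading, the second patient stays in the denominator and lowers the arm's rate.

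At stake is the reported proportion with hyponatremia, which could be understated in one arm or both, and unequally. The trial is open-label, so the scoring of a value below 125 is better settled before the results are seen than decided case by case afterwards. The total urine output comparison does not depend on it.

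**Working it through.** The plan states no figure for this endpoint, so there is none to reproduce. The check has three parts.

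**1. Apply the rule.** The literal rule is 125 ≤ Na ≤ 135. The comparison rule keeps the plan's upper limit and drops the floor: Na ≤ 135.

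| 24-hour Na (mEq/L) | Literal rule | No floor |
|---|---|---|
| 120 | non-event | event |
| 124 | non-event | event |
| 125 | event | event |
| 130 | event | event |
| 135 | event | event |
| 136 | non-event | non-event |

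The two rules differ only below 125, where the literal rule gives the same score as at 136.

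**2. How many patients could be affected.** From the plan: 30 patients at 1:1, so 15 per arm. One misclassified patient moves the arm's proportion by 1/15 = 6.7 percentage points.

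The plan gives no sodium mean or SD. Those below are assumptions, with a normal distribution, and p is the probability that a patient falls below 125:
- p = Φ((125 − mean)/SD)
- expected number = 30p
- chance of at least one = 1 − (1 − p)^30
- chance of two or more in the same arm (either arm) = 1 − (1 − a)², where a is the binomial probability of at least two among 15

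| Mean, SD | (125 − mean)/SD | Expected of 30 | At least one | Two or more in one arm |
|---|---|---|---|---|
| 133, 5 | −1.60 | 1.64 | 82% | 36% |
| 133, 4 | −2.00 | 0.68 | 50% | 9% |
| 135, 4 | −2.50 | 0.19 | 17% | 0.8% |
| 135, 3 | −3.33 | 0.01 | 1% | <0.1% |
| 137, 3 | −4.00 | 0.001 | 0.1% | <0.1% |

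**3. What reclassification does to the test.** These are illustrative counts at 15 per arm, with two-sided Fisher p-values.

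| Literal rule | No floor | Reclassified |
|---|---|---|
| 4 v 4, p = 1.00 | 4 v 5, p = 1.00 | one patient |
| 4 v 4, p = 1.00 | 4 v 6, p = 0.70 | two in one arm |
| 5 v 2, p = 0.39 | 5 v 5, p = 1.00 | three in one arm |
| 5 v 0, p = 0.04 | 5 v 1, p = 0.17 | one patient |

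In the first three rows the rate changes and the test conclusion at 0.05 does not. The last row shows that this is not general: from a lopsided table, one patient can move p across 0.05.

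**The case against.** The strongest objection is that the text may be damaged. The definition ends in a 24 that has no evident meaning. It cannot be a citation to the printed reference list, which stops at 16. It may be a timing fragment, a drafting slip or an artefact of text extraction, and if words were lost there, a grade label or a line for values below 125 could have gone with them. This stands as a caveat. The two bounds are legible, however, and nothing elsewhere supplies the missing category.

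Second, the range may be deliberate, describing mild-to-moderate hyponatremia. The plan does not say so: the outcome carries no grade and no severe category accompanies it. If a grade was meant, the label and the missing category still need an edit.

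Third, scoring such a patient as a non-event is an inference. The plan states no denominator for this outcome, and an investigator reading the chart might not file 122 as normal. That is true. But no rule removes such a patient, so keeping the patient in the denominator as a non-event is the plain reading.

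Fourth, the consequence is slight: one secondary outcome in a 30-patient pilot, with an 83% chance at mean 135 and SD 4 that no patient is affected. This stands in full. It limits the weight of the point but does not make the definition right.

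**Conclusion.** The concern holds as a literal reading of the endpoint. The definition reverses its own ordering below 125, its neighbours in the same list do not, and no other provision compensates.

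The likely effect is small and may be nil: 6.7 percentage points of an arm's rate per affected patient, with between about 0.001 and 1.6 of the 30 patients expected to be affected. That range rests on an assumed normal distribution with mean 133 to 137 and SD 3 to 5, none of which comes from the plan, and on all 30 patients being enrolled 15 to an arm and assessed. The Fisher counts are illustrations, not forecasts. For example, an assumed mean of 135 puts about half of patients at or below 135, which is more than 4 of 15.

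The point should be corrected because the definition is wrong as written and the correction is nearly free. It does not threaten the trial's main result.

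**What to change.** In the Endpoints section:

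- Define hyponatremia as sodium ≤135 mEq/L at 24 hours after the metolazone dose, with no lower bound. This keeps the plan's own upper limit.
- Report the number of patients with sodium below 125 in each arm as a separate descriptive line. If a mild-to-moderate grade was intended, this line supplies the missing category, and the 125 to 135 count can be recovered by subtraction.
- Remove or explain the stray 24.

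The cost is one line of text. The change uses the 24-hour sodium value the endpoint already requires, needs no baseline value, and alters only outcome scoring. It should be made before outcome data are examined.
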